There was no change in CCR5 virus susceptibility to PRO 140 following treatment. All subjects had CCR5-only virus at screening in the first-generation Trofile assay. CCR5-only tropism results were observed in all subjects at all other timepoints, with two exceptions: One of nine (11%) of placebo subjects had dual/mixed virus at baseline and all subsequent timepoints, reflecting a spontaneous and stable switch in co-receptor tropism results. One of 30 (3%, 0.5 mg/kg group) had a dual/mixed tropism result on day 8 and CCR5-only results at all other timepoints, including the end of the day [Jacobson JM, 2008]. Clonal analysis of the dual/mixed virus revealed that it reflected outgrowth of pre-existing undetected virus rather than mutation of a CCR5 virus to a dual/mixed virus following treatment [Marozsan, 2008]. Therefore, no significant development of viral resistance to PRO 140 was observed despite potent and prolonged (2-3 weeks on average) viral suppression, followed by slow washout of the drug. Given that resistance to other classes of HIV-1 drugs can develop within one week of monotherapy [Demeter LM, 2000] [Saag, 1993][Richman, 1994], the findings indicate that PRO 140 presents a high barrier to viral resistance in vivo.

Figure 1-3 illustrates the mean serum concentrations of PRO 140 after IV injection. Serum levels increased with increasing dose. The mean Area Under Curve (AUC) from time zero to infinity (AUC_{∞}) values were 11.1, 74.3 and 278 mg x day/L for the 0.5, 2 and 5 mg/kg groups. The mean

serum half-life was 3.5-3.9 days in the two highest dose groups. In addition, PRO 140 significantly masked CCR5 on circulating lymphocytes for 2-4 weeks [Jacobson JM, 2008]. The PK and receptor occupancy data were broadly consistent with the duration of antiviral effects.

Figure 1-3: PRO 140 1302 Study: PRO 140 serum concentrations following a single intravenous injection in HIV- infected individuals.

The figure illustrates the mean serum concentrations over time by treatment group. The error bars depict standard deviations. The mean serum half-lives were 3.9 days and 3.5 days in the 2 mg/kg and 5 mg/kg dose groups, respectively.

[figure not shown]

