1.4.2.7 PRO 140_CD01 Study

PRO 140_CD01 study (open-label, 43 subjects, multi-center) (12-cohort 1, 28-cohort 2, 3-cohort 3) evaluated the efficacy, safety, and tolerability of PRO 140 monotherapy (350 mg subcutaneous injection weekly for up to 12 weeks) for the maintenance of viral suppression following substitution

of antiretroviral therapy in HIV-1 infected patients (with exclusive CCR5-tropic virus). Participants in this study were experienced HIV-infected individuals who were virologically suppressed on combination antiretroviral therapy. Consenting patients were shifted from combination antiretroviral regimen to PRO 140 monotherapy for 12 weeks.

Forty (43) subjects (M/F: 40/3) with median age of 55.5 years (26-72) and median CD4 T-cell count of 604.5 cells/mm³ (365-1240) were enrolled in the CD01 study. Overall, twenty-three out of 43 (54%) enrolled subjects completed 12 weeks of PRO140 monotherapy without experiencing virologic failure. Virologic failure was defined as two consecutive HIV-1 RNA levels \geq 400 copies/mL separated by at least 3 days.

Of the first 40 enrolled subjects enrolled under cohort 1 and cohort 2, three subjects were found to have Dual/Mixed (D/M) tropism [1 at baseline and 2 at the time of virologic failure] and 40 subjects were found to have exclusive CCR5-tropic virus. A letter of amendment was filed to increase the planned number of subjects from 40 to 43 subjects to compensate for the 3 Dual/Mixed subjects enrolled in the study.

All virologic failure subjects who had available lab data in both studies achieved viral suppression to < 400 HIV-1 RNA copies/mL, as well as viral suppression to 'Non Detectable' or < 50 HIV-1 RNA copies/mL after re-initiation of ART.

The by-subject analysis of PhenoSense® Entry Assay data for PRO140, maraviroc, and AMD3100 shows no significant changes in the post-treatment IC50 and IC90 values were noted when compared with baseline values in virologic failure and non-virologic failure groups of subjects.

Anti-PRO140 antibodies were not identified in any available post-treatment sample and data derived from the CD01 study further supports the favorable PRO140 PK profile data generated from both pre-clinical as well as prior Phase 1/2 clinical trials.

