7.11.7 HIV-1 Trofile® Assay

- Includes:
 - a. Trofile® RNA AssayTrofile® RNA is the primary assay used to assess HIV-1 co-receptor tropism status.
- Frequency of testing: At Virologic Failure visit

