8.2 DESCRIPTION OF SAFETY MEASURES

The following safety measures will be assessed in this study.

1. Mean change in viral load (HIV-1 RNA levels) at the conclusion of the treatment period
2. Mean change in CD4 cell count at the conclusion of the treatment period
3. Emergence of Dual/Mixed (D/M)- and CXCR4-tropic virus in patients who had exclusive CCR5-tropic virus at study entry.
4. Tolerability of repeated subcutaneous administration of PRO 140 as assessed by investigator-evaluation of injection site reactions
5. Frequency of treatment-related adverse events resulting in study drug discontinuation
6. Frequency of Grade 3 or 4 adverse events as defined by the DAIDS Adverse Event scale
7. Frequency of treatment-emergent serious adverse events

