6. DATA CONVENTION AND RELATED DEFINITIONS

6.1 Baseline Definition

Baseline for a given parameter or endpoint is defined to be the baseline of CD02 or CD02_OpenLabel study.

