7.2.3 Emergence of Dual/Mixed (D/M) - and CXCR4-tropic virus

The data for this outcome measure will be provided by external vendor Monogram Biosciences. All patients have exclusive CCR5-tropic (i.e., R5 or X4) virus at study entry. The proportion of subjects with any tropism result of dual/mixed will be summarized.

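### SAP 7.2.3 counts any dual/mixed tropism result as emergence without comparing it with the parent-study baseline, so a subject already dual/mixed at entry would be counted

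*SAP*

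**What the plan says.** Protocol 8.2 defines the outcome conditionally: "Emergence of Dual/Mixed (D/M)- and CXCR4-tropic virus in patients who had exclusive CCR5-tropic virus at study entry". The synopsis, Protocol 2 and 8.7.4, and SAP 2.4 carry the same condition.

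SAP 7.2.3 handles it differently. It first asserts: "All patients have exclusive CCR5-tropic (i.e., R5 or X4) virus at study entry". It then gives the counting rule: "The proportion of subjects with any tropism result of dual/mixed will be summarized". SAP 7.2 places all outcome measures on the safety population.

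Three other places bear on what reference is available:

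- Protocol 7.11.7, on Trofile: "Frequency of testing: At Virologic Failure visit". Both schedules of assessments agree, and no eligibility criterion in Protocol 3.3 concerns tropism.
- SAP 6.1: "Baseline for a given parameter or endpoint is defined to be the baseline of CD02 or CD02_OpenLabel study".
- SAP 7.2.9.4 provides by-subject listings of the Trofile data.

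**The concern.** The outcome asks whether tropism changed during PRO 140 treatment in subjects who began with CCR5-only virus. That needs a reference result and a rule for change. SAP 7.2.3 has neither: it takes the entry condition as true for everyone and counts the later result alone.

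The assertion is also unusable as written. X4 denotes CXCR4-using virus, so a gloss that admits R5 or X4 cannot describe exclusively CCR5-tropic virus. In addition, the rule names only dual/mixed results, although the section title and the outcome also cover CXCR4 virus.

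What is at stake is the meaning of a small count. A subject already dual/mixed before PRO 140 and a subject whose result changed during treatment would both appear under emergence, and the first falls outside the protocol's definition.

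**Working it through.** The plan gives no expected proportion, power or sample size for this outcome, so it has no figure to reproduce. The two percentages in the study 1302 background (Protocol 1.4.2.4) do check: 1/9 = 11% and 1/30 = 3%.

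**Can the entry assertion fail?** Protocol 1.4.2.4 says all 1302 subjects were CCR5-only at screening, yet one placebo subject "had dual/mixed virus at baseline and all subsequent timepoints". Protocol 1.4.2.7 reports for the first 40 subjects of CD01, a study in exclusively CCR5-tropic infection: "three subjects were found to have Dual/Mixed (D/M) tropism [1 at baseline and 2 at the time of virologic failure". That report makes the split between baseline and failure that SAP 7.2.3 omits.

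**Effect of the rule on those counts.**

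| Study | Any dual/mixed (SAP rule) | Baseline dual/mixed subject excluded (protocol condition) |
|---|---|---|
| CD01, first 40 | 3/40 = 7.5% | 2/39 = 5.1% |
| 1302 | 2/39 = 5.1% | 1/38 = 2.6% |

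With all 43 CD01 subjects as denominator, the pair is 3/43 = 7.0% and 2/42 = 4.8%.

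**Chance of a miscounted subject here.** Inputs:

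- Rate of dual/mixed virus at baseline despite CCR5 selection (assumed to carry over): (1 + 1)/(39 + 40) = 2/79 = 2.53%.
- Number tested at VF, m (assumed, since the documents give no expected failure rate): 5 to 10.
- VF is taken as unrelated to entry tropism.

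P(at least one) = 1 − (1 − 2/79)^m:

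- m = 5: 1 − 0.9747^5 = 12%
- m = 10: 1 − 0.9747^10 = 23%

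**Precision.** The exact 95% interval for CD01 alone (1/40) is 0.06% to 13.2%. At the lower end, the chance for m = 5 to 10 is 1 − 0.9994^5 = 0.3% to 1 − 0.9994^10 = 0.6%. At the upper end it is 1 − 0.8684^5 = 51% to 1 − 0.8684^10 = 76%. The 12% to 23% is therefore an order of magnitude only.

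**Size of one case.** SAP 7.2 uses the safety population, and the synopsis plans up to 50 subjects. One miscounted subject moves the figure from 0/50 = 0% to 1/50 = 2%.

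**Is the parent baseline applied?** SAP 7.2.1 and 7.2.2 both analyse change from baseline; 7.2.3 does not mention baseline. Where the SAP draws on parent data for antiretroviral therapy (7.1.5), it says so; no such sentence names tropism. The rule also has no time window. If parent results were merged in, a baseline dual/mixed result would itself meet it.

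**The case against.** The strongest reply is that a reference already exists. SAP 6.1 covers every parameter and endpoint, Protocol 7.5 carries HIV history forward, and Protocol 4.1 retains subject numbers. A reader might infer that entry tropism is neither tested nor imported. The documents do not support the second half: a general import rule is there. What stands is narrower: 7.2.3 does not invoke that rule, name a parent tropism result or define a change.

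Second, both parent populations are described as CCR5-tropic, so the SAP sentence may simply restate that selection. No document shows a subject in this study with dual/mixed virus at entry. A reader might conclude that pre-existing virus is being reported as emergent. The documents support only that it would be, if such a subject entered and was tested at VF.

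Third, the rate is weak. It pools two studies that each had a case. The 1302 screen used a first-generation assay, and the CD01 text does not reconcile (3 dual/mixed plus 40 CCR5-only among the first 40). Carrying the rate over to subjects suppressed on PRO 140 plus background therapy is an assumption. All of this stands, and it is why the probability is only illustrative.

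Fourth, the study is descriptive, no inference is planned for safety data in SAP 7.2.4, and every Trofile result is listed. A careful reader could find the dual/mixed results at VF, but could not judge emergence from them without the reference.

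**Conclusion.** The point holds in conditional form. The counting rule in SAP 7.2.3 does not match the outcome in Protocol 8.2, which applies only "in patients who had exclusive CCR5-tropic virus at study entry". A subject with dual/mixed virus already detected at the parent baseline, and tested at VF, would be counted as emergent. The chance of at least one is about 12% to 23% if 5 to 10 failures are tested. That rests on the 2/79 rate carrying over and on failure being unrelated to entry tropism. The effect of one case is 2 percentage points of 50.

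Two larger figures may tempt a reader:

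- 1 − (1 − 2/79)^50 = 72% is the chance that at least one of 50 enrolled subjects carries such virus. Only those tested at VF can be counted, so it is not the chance of a wrong count.
- A shift from 0% to 10–20% (1/10 to 1/5) uses tested subjects as the denominator, whereas SAP 7.2 uses the safety population.

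Nor would a baseline comparison separate every outgrowth of earlier virus from a true switch. The 1302 subject whose dual/mixed virus was traced by clonal analysis to undetected earlier virus had CCR5-only results at every timepoint except day 8, and would still count as emergent.

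**What to change.** Rewrite SAP 7.2.3 as follows:

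- Name the last parent-study tropism result before the first PRO 140 dose as the reference, consistent with SAP 6.1.
- Restrict the analysis to subjects with a documented CCR5-only reference.
- Count emergence only as a change from that reference to dual/mixed or CXCR4.
- Show a table of reference by VF result.
- List subjects with a non-CCR5 or missing reference separately.
- Delete the parenthesis that glosses CCR5-tropic as R5 or X4.

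The cost is SAP wording and a merge of parent-study tropism data under the retained subject numbers, provided those results are on file. No new visits or samples are needed. The denominator becomes slightly smaller. The change removes only dual/mixed virus detected at the reference, not undetected minority virus, and the SAP should say so.

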7.2.4 Analysis of Safety Data

The Safety population will be used for the analysis of safety endpoints. No inferential statistics are planned.

7.2.4.1 Adverse Events

Adverse events will be classified by system organ class and preferred term (PT) according to the most recent MedDRA dictionary.

Since this is an extension of the PRO 140_CD 02 study, all adverse events (AE) that captured in this study will be considered as Treatment Emergent Adverse Events (TEAEs). The following TEAE summaries will be provided, using frequency counts and percentages:

- Overall (i.e., regardless of severity or relationship to treatment)
- By severity grade (mild, moderate, severe, life threatening or death)
- By relationship to study treatment

In addition, separate summaries of SAEs, and AEs resulting in discontinuation of study treatment will be presented.

Unless otherwise specified, at each level of subject summarization, a subject will be counted only once. If there is more than one occurrence of an event, the event of the worst severity or the worst-case relationship category will be summarized.

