3 STUDY DESIGN

This is an extension study, to provide continued access to PRO 140 to subjects who complete participation in PRO140_CD02 or CD02_OpenLabel and continue to receive clinical benefit and would require PRO 140 to form a viable regimen, in the opinion of the treating physician. The patient population for this trial is treatment-experienced HIV-infected patients with CCR5-tropic virus who demonstrate evidence of HIV-1 suppression after successfully completed 24 weeks of treatment in the PRO140_CD02 or CD02_Open Label study.

Subjects participating under Protocol versions 1.0-3.0 received 350 mg of PRO 140. Dose was increased from 350 mg to 700 mg weekly to provide maximum viral load suppression in a heavily treatment experienced population to avoid developing resistance to current OBT therapies.

Those that were enrolled under version 1.0-3.0 have the option of remaining on their current dose of 350mg or increasing their dose to 700 mg for the remainder of the trial.

The study is divided into three phases: Screening, Treatment Extension and Follow-up.

Screening Phase begins with signing of Informed Consent and lasts up to 21 days. All subjects will continue taking PRO 140 SC injection in addition to OBT during the Screening Phase.

Subject will enter the Treatment Extension Phase as soon as HIV-1 viral load results are available for review by Investigator. Treatment Extension Phase consists of weekly study treatment injections along with OBT. Study participants will be regularly monitored for viral load and will cease weekly study treatment injections should they experience virologic failure. Virologic failure is defined two consecutive HIV-1 RNA levels ≥ 400 copies/mL.

Note: Subjects will be allowed to continue PRO 140 with existing OBT regimen while waiting for new regimen to be constructed by the Investigator.

Subjects who experience virologic failure at any point during the Treatment Extension Phase will undergo the Virologic Failure (VF) Visit assessments and will be followed up every 4 weeks until viral suppression is achieved (i.e., plasma HIV-1 RNA levels below level of detection) or up to a maximum of 6 months after cessation of therapy if the treating physician does not feel that there is an antiretroviral regimen that will regain full viral suppression. Subjects who do not experience virologic failure, will be followed up every 2 weeks for total of 4 weeks.

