4.3 FOLLOW-UP PHASE

The duration of follow-up depends on whether subject experiences virologic failure.

- Subjects who experience virologic failure within the Treatment Extension Phase will be followed up every 4 weeks until viral suppression is achieved (i.e., plasma HIV-1 RNA levels below level of detection) or up to a maximum of 6 months after cessation of therapy if the treating physician does not feel that there is an antiretroviral regimen that will regain full viral suppression.
- Subjects who do not experience virologic failure at the end of the Treatment Extension Phase, will be followed up every 2 weeks for total of 4 weeks.

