8.7.5.1 Adverse Events

Adverse events will be coded using Medical Dictionary for Regulatory Activities (MedDRA). TEAEs are defined as events with an onset on or after the first treatment. TEAEs will be summarized by treatment group, System Organ Class, and preferred term. The following TEAE summaries will be provided:

- TEAEs by severity grade
- TEAEs by relationship to study treatment.

In addition, separate summaries of SAEs, and AEs resulting in discontinuation of study treatment will be presented.

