9.1.1 Reporting of Adverse Events

Report initiation for all AEs and SAEs will begin at the time of the first treatment extension visit and continue up until the final study visit (i.e. up to NVF-FU2 for subject who do not experience virologic failure or until viral suppression is achieved for subjects who experience virologic failure). All events will be followed to resolution or until 30 days after the subject completes the study. A final assessment of outcome will be made at that time.

All AEs must be recorded in the subject's medical records and on the eCRFs. AEs will be reported using customary medical terminology along with the following information: the onset and end dates, whether the event is considered to be a SAE (see [Section 9.2](#)), the impact the event had on study treatment (see [Section 9.1.2](#)), the DAIDS AE grade (intensity) of the event (see [Section 9.1.3](#)), the causality of the event (see [Section 9.1.4](#)), whether treatment was given as a result of the event (see [Section 9.1.5](#)), and the outcome of the event (see [Section 9.1.6](#)).

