- Subjects who experience virologic failure within Treatment Extension Phase will be followed up every 4 weeks until viral suppression is achieved (i.e., plasma HIV-1 RNA levels below level of detection) or up to a maximum of 6 months after cessation of therapy if the treating physician does not feel that there is an antiretroviral regimen that will regain full viral suppression.
- Subjects who do not experience virologic failure at the end of Treatment Extension Phase, will be followed up every 2 weeks for total of 4 weeks.

Figure 2-1 Clinical Trial Flow Diagram

Study Duration

- **Screening Phase:**
 - up to 21 days
- **Treatment Extension Phase:**
 - weekly (\pm allowed windows) until subject withdraws consent, experience virologic failure or PRO 140 is approved or CytoDyn decides to discontinue its development
- **Follow-up Phase:**
 - weeks* (\pm allowed windows)
*or up to maximum of 6 months after experiencing Virologic Failure (VF) if the treating physician does not feel that there is an antiretroviral regimen that will regain full viral suppression.

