- [1] Subject will be followed up till the viral suppression is achieved or up to a maximum of 6 months after experiencing Virologic Failure (VF) if the treating physician does not feel that there is an antiretroviral regimen that will regain full viral suppression.
- [2] Symptom-directed physical examination

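### The TEAE definition has no end date, so the crude adverse event percentages mix time on and off PRO 140 over windows that depend on virologic failure

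*SAP*

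**What the plan says.** SAP 7.2.4.1 gives the analysis rule: "all adverse events (AE) that captured in this study will be considered as Treatment Emergent Adverse Events (TEAEs". It plans frequency counts and percentages of TEAEs overall, by severity grade and by relationship, with separate summaries of SAEs and of AEs leading to discontinuation. Each subject is counted once, at the worst severity or relationship. No on-treatment and post-treatment split is planned.

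Protocol 8.7.5.1 bounds the definition at one end only: "TEAEs are defined as events with an onset on or after the first treatment".

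Protocol 9.1.1 sets how long AEs are collected. It runs "up to NVF-FU2 for subject who do not experience virologic failure" (the visit that Table 4-2(a) calls NVF-EFU2, 4 weeks ±3 days after EOT2), and "until viral suppression is achieved for subjects who experience virologic failure". Table 4-2(b) and SAP Table 8-2 have AE rows at the follow-up visits 4, 8 and 12 weeks after failure. Protocol 4.3 allows this follow-up to run "up to a maximum of 6 months after cessation of therapy" if the physician sees no regimen that will restore full suppression, and SAP 2.2 repeats this. SAP Appendix 1 starts the same clock elsewhere: "up to a maximum of 6 months after experiencing Virologic Failure (VF").

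On treatment after failure, Protocol section 3 says that subjects "will cease weekly study treatment injections should they experience virologic failure". A note there allows PRO 140 to continue until the investigator has built a new regimen.

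**The concern.** A treatment-emergent table is read as describing the period in which the study drug could plausibly act. Here the label covers everything collected, and collection continues after PRO 140 stops. The length of that tail is set by an outcome of the study: short and fixed without virologic failure, open or up to 6 months with it. Subjects who fail may also be on a changed antiretroviral regimen.

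Two things are at stake. First, a crude percentage has no stable meaning when the time at risk differs by outcome and nothing adjusts for it. Second, because each subject is counted at worst severity, one off-drug Grade 4 event replaces that subject's milder on-drug events in the severity table. With up to 50 subjects planned, one subject is at least 2 percentage points. Grade 3 or 4 AEs are an outcome measure in both documents, and treatment-emergent SAEs are one in Protocol 8.2.

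**Working it through.** The documents state no TEAE rate, power or sample size for this point, so there is no plan figure to reproduce. The check sets the rules side by side and then bounds their effect.

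**1. Is there an end bound anywhere?** SAP 7.2.4.1 has none. Protocol 8.7.5.1 has a start only. Protocol 9.1.1 limits collection, not the definition, and for failures it names viral suppression without a calendar cap.

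**2. Off-drug collection by outcome.**
- No failure: 28 ±3 days after EOT2, so at most 28 + 3 = 31 days.
- Failure with a workable new regimen: until suppression, for a duration the documents do not state.
- Failure with no fully suppressive regimen foreseen: up to 6 months. The clock starts at cessation of therapy in Protocol sections 3, 4 and 4.3 and in SAP 2.2 (follow-up text). It starts at virologic failure in Protocol 5.1, Table 4-2 and the synopsis duration item, and in SAP 2.2 (study duration) and Appendix 1. If PRO 140 continues after failure, the second anchor leaves less off-drug time.

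**3. Ceiling on off-drug time.** Taking 6 months as 183 days from cessation, (183 − 28)/183 = 155/183 = 85% of follow-up lies beyond day 28. Using the 3.5 to 3.9 day half-life in Protocol 1.4.2.4 (single IV doses; applying it to weekly SC dosing is an assumption):
- 28/3.9 to 28/3.5 = 7.2 to 8.0 half-lives
- 183/3.9 to 183/3.5 = 46.9 to 52.3 half-lives

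Serum level is not the whole story. Protocol 1.4.2.5 reports receptor occupancy above 85% for 29 days after single IV doses of 5 and 10 mg/kg. Late follow-up is therefore essentially drug-free in serum, but day 28 is not a clear end of effect.

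**4. Illustrative effect on the SAE percentage.** Assume a constant SAE hazard taken from the CD01 study (1 of 43 subjects; total treatment duration 14 weeks, Table 1-1), the same on and off drug, with every failing subject followed for 26 weeks off drug.

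h = −ln(1 − 1/43)/14 per week; P(at least one SAE) = 1 − exp(−h × weeks observed).

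For one failing subject:
- 24 weeks on drug: 4.6% with a 4-week tail (28 weeks) and 8.1% with all captured time (50 weeks). Off-drug share of time: 26/50 = 52%.
- 52 weeks on drug: 9.0% and 12.3%. Off-drug share: 26/78 = 33%.

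For the cohort, all-captured P = (1 − f) × P(4-week tail) + f × P(26-week tail), where f is the share who fail:

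| Weeks on drug | 4-week tail for all | f = 10% | f = 30% | f = 50% |
|---|---|---|---|---|
| 24 | 4.60% | 4.94% | 5.64% | 6.33% |
| 52 | 8.98% | 9.31% | 9.97% | 10.63% |

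In 50 subjects with 24 weeks on drug, the shift is 50 × 0.0034 = 0.17 of a subject at f = 10% and 50 × 0.0173 = 0.87 at f = 50%. The failure share, exposure times and equal hazard are assumptions; a different hazard on a changed regimen would alter the result.

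**The case against.** The strongest reply is that treatment-emergent is a timing label, not an attribution. Protocol 9.1.4 has the investigator judge causality event by event, taking other therapies into account. The SAP tabulates TEAEs by relationship, and treatment-related AEs leading to discontinuation are a separate outcome. All subjects take background therapy of three or more agents, so no window isolates PRO 140. The study is single-arm, SAP 7.2.4 plans no inferential safety statistics, and counting too much is the cautious direction for safety. This stands in part. The relationship table does separate events judged unrelated, but the overall, severity and SAE summaries still mix periods.

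A reader might infer that failing subjects spend six months off drug on a new regimen, with that regimen's toxicity charged to PRO 140. The documents do not support that pairing. The 6-month maximum applies when the physician foresees no fully suppressive regimen; subjects with a workable one are followed to suppression, for an unstated time. Continued PRO 140 and the second anchor can shorten the off-drug period further, so 85% is a ceiling and not a typical value.

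A hard cut at day 28 would also be hard to defend, given the 29-day receptor occupancy and the ±3-day window at NVF-EFU2.

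Two details of scope also stand. The SAP outcome list (2.4) has no SAE item, and the Grade 3 or 4 outcome carries no treatment-emergent qualifier in either document. Nor is the gap the SAP's alone: the protocol definition is open-ended too.

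**Conclusion.** The point holds as a gap in definition. Followed as written, the plan yields crude TEAE, severity-grade and SAE percentages that combine on-drug and off-drug events over windows that differ by virologic outcome. Nothing elsewhere in the two documents closes the window.

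The effect cannot be determined from the documents and is probably modest: less than one subject in 50 across the scenarios above, although any single late severe event moves a table cell by at least 2 percentage points. That estimate rests on the borrowed CD01 rate and full 26-week follow-up for every failing subject. The documents do not support the further conclusion that PRO 140's safety profile would be materially misstated. The change is worth making because it is cheap and loses no safety data.

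**What to change.** In SAP 7.2.4.1, with Protocol 8.7.5.1 aligned to it, define a TEAE as an event with onset from the TE1 dose to the last actual PRO 140 dose, including any doses given while a new regimen is being built, plus a fixed window equal for all subjects. The window should cover the NVF-EFU2 visit window and the reported 29-day receptor occupancy; 31 days (28 + 3) does both when the last dose is given at EOT2. If the last dose came earlier, new events at late follow-up visits go to the post-treatment table under the same rule.

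Tabulate later events, including SAEs and Grade 3 or 4 AEs, in a separate post-treatment table. Keep all AEs in the listings and in an all-captured-events total. The places that start the 6-month clock at cessation of therapy and at virologic failure must be reconciled; this note takes no position on which is right.

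The cost is one definition in the SAP, the matching protocol wording and one extra table, settled before database lock. A few late events leave the headline table but remain reported. Visits, dosing and data collection do not change.
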